2. LIST OF ABBREVIATIONS

Term	Definition / description
AE	Adverse Event
ANCOVA	Analysis of Covariance
BRPM	Blinded Report Planning Meeting
CI	Confidence Interval
CR	Complete Response
CTC	Common Terminology Criteria
CTP	Clinical Trial Protocol
CTR	Clinical Trial Report
DM&SM	Boehringer Ingelheim Data Management and Statistics Manual
DMC	Data Monitoring Committee
EMA	European Agency for the Evaluation of Medicinal Products
HLT	High Level Term
HRQoL	Health-Related Quality of Life
ICH	International Conference on Harmonisation
MedDRA	Medical Dictionary for Regulatory Activities
NE	Not Evaluable
NN	Non-CR/Non-PD
OS	Overall Survival
PD	Progressive Disease
PFS	Progression Free Survival
PK	Pharmacokinetics
PSTAT	Project Statistician
PR	Partial Response
PT	Preferred Term
PV	Protocol Violation
Q1	Lower Quartile
Q3	Upper Quartile
s.d.	Standard Deviation
SD	Stable Disease
SMQ	Standardised MedDRA query

Term	Definition / description
SOC	System Organ Class
TEAE	Treatment Emergent Adverse Event
TOC	Table of Contents
TMW	Trial Medical Writer
TSAP	Trial Statistical Analysis Plan

3. INTRODUCTION

As per ICH E9, the purpose of this document is to provide a more technical and detailed elaboration of the principal features of the analysis described in the protocol, and to include detailed procedures for executing the statistical analysis of the primary and secondary variables and other data.

This TSAP assumes familiarity with the Clinical Trial Protocol (CTP), including Protocol Amendments. In particular, the TSAP is based on the planned analysis specification as written in CTP Section 7 “Statistical Methods and Determination of Sample Size”. Therefore, TSAP readers may consult the CTP for more background information on the study, e.g., on study objectives, study design and population, treatments, definition of measurements and variables, planning of sample size, randomization.

SAS[®] Version 9.2 will be used for all analyses.

4. CHANGES IN THE PLANNED ANALYSIS OF THE STUDY

Tumour shrinkage measurement is changed to the maximum decrease of sum of target lesion diameters (i.e. the minimum sum of target lesion diameters after randomisation minus baseline) for better interpretability.

5. ENDPOINTS

5.1 PRIMARY ENDPOINT

The primary endpoint of this study is progression-free survival, as determined by RECIST 1.1 (1).

5.2 SECONDARY ENDPOINTS

5.2.1 Key secondary endpoint

The key secondary endpoint is overall survival.

5.2.2 Other secondary endpoints

Refer to Section 5.1.1 of the CTP.

Other secondary endpoints of this trial are:

- Objective response (CR, PR) according to RECIST 1.1 (1)
- Disease control (CR, PR, SD) according to RECIST 1.1 (1)
- Tumour shrinkage
- Health-related Quality of Life (HRQoL)

6. GENERAL ANALYSIS DEFINITIONS

6.1 TREATMENTS

For reporting purposes, all randomised patients will be classified into either ‘Afatinib’ or ‘Erlotinib’ as randomised. For efficacy analyses patients will be analysed as randomised. For safety analyses, treated patients will be analysed according to the initial treatment taken.

The following study periods based on actual start and stop dates of study treatment administration are defined:

- Pre-screening: for any data recorded prior to day of informed consent.
- Screening: day of informed consent to day prior to starting study treatment.
- On-treatment: day of first administration of study treatment to the 28th day after last administration of study treatment.
- Post-treatment: day after last administration of study treatment to the 28th day after last administration of study treatment.
- Post-study: on or after the 29th day after last administration of study treatment.

For safety summaries data recorded up to 28 days after last administration of study treatment will be considered as on-treatment (i.e. the actual on-treatment and post-treatment periods defined above will be combined into one ‘on treatment’ analysing treatment), unless otherwise specified according to the protocol Section 5.2.2.2 and protocol Appendix 10.7.

6.2 IMPORTANT PROTOCOL VIOLATIONS

No per protocol set (PPS) will be defined for this study; however patients with potentially important protocol violations (IPVs) will be documented. The following list of potentially IPVs will be used; note that this is a working list and may not be finalised until the final Blinded Report Planning Meeting (BRPM) prior to database lock.

Table 6.2: 1 Important protocol violations

Category/code		Description	Comment
A		Entrance criteria not met	
	A1	Diagnosis of NSCLC questionable	Refer to IN 1
	A2	Prior treatment for NSCLC does not meet entrance criteria	Refer to IN 2,3, EX 1,2
	A3	No measurable disease according to RECIST 1.1 at screening	Refer to IN4
	A4	Abnormal screening values	Refer to IN7
	A5	Other deviation from entrance criteria	Refer to in/exclusion criteria
B		Informed consent	
	B1	Informed consent not available	Signed informed consent not available
	B2	Inadequate informed consent	Informed consent obtained but not adequately done (e.g., obtained after the study specific activities were done, patient signed the wrong version of the ICF, version signed did not receive prior IRB/EC approval).
C		Trial medication & randomization	

	C1	Incorrect medication dose taken	e.g., starting dose is not 40 mg for afatinib or 150 mg for erlotinib; dose was not paused, resumed, reduced, or discontinued according to protocol, including incorrect dose interruptions during concomitant treatment
	C2	Randomization not followed	e.g., randomized to afatinib but received erlotinib or vice versa.
	C3	Non-compliance	Check MQRM listings for extreme non-compliance only
D		Concomitant medication	
	D1	Use of prohibited concomitant medications	Review concomitant medications for prohibited medication use.
E		Trial specific	
	E1	Procedures not performed according to protocol	Check applicable data.
	E2	Prohibited on study interventions given	Patient received therapeutic radiation or another anti-cancer treatment during on study period

6.3 PATIENT SETS ANALYSED

- Randomised set:
 This patient set includes all randomised patients, whether the patient received study medication or not.
- Treated set:
 This patient set includes all patients who received at least one dose of investigational treatment.

Ranomised set will be used for all efficacy analyses and treated set will be used for all safety analyses.

6.5 POOLING OF CENTRES

This section is not applicable because centre/country is not included in the statistical model.

6.6 HANDLING OF MISSING DATA AND OUTLIERS

In general missing efficacy data will not be imputed and all reasonable efforts will be taken during the study to obtain such data. Patients with unknown vital status, missing tumour imaging data and missing HRQOL assessments will be censored for time to event analyses; further details are provided in [Section 7](#).

Missing or incomplete AE dates are imputed according to BI standards (see “Handling of missing and incomplete AE dates”). [\(2\)](#)

6.7 BASELINE, TIME WINDOWS AND CALCULATED VISITS

Baseline values will be the measurements taken most recently prior to first administration of study drug.

Study day will be calculated relative to the date of the first administration of study drug. The day prior to first administration of study drug will be ‘Day -1’ and the day of first administration of study drug will be ‘Day 1’; therefore ‘Day 0’ will not exist.

For the presentation of tumour response data which will follow a calculated visit approach based on the protocol specified tumour imaging schedule. Imaging will be performed at week 8, 12 and 16, and in 8-weekly intervals thereafter from the date of randomisation; images will be slotted to Week 8, 12, 16, 24, ... XX based on their relative day and using a $\pm 2, \pm 4$ week window as appropriate (images taken in the first 4 weeks from randomisation will be slotted to Week 8). If two or more images for a patient are assigned to one interval then the last assessment will be used to ensure progressive disease is not missed. Note German sites only will have an X-ray completed instead of a CT or MRI for the week 12 assessment. If disease progression is suspected, a follow-up CT or MRI will then be completed. In the case where a CT or MRI is not completed for the week 12 assessment, it will be handled as missing assessment.

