**Proprietary confidential information.**

© 2016 Boehringer Ingelheim International GmbH or one or more of its affiliated companies. All rights reserved.

This document may not - in full or in part - be passed on, reproduced, published or otherwise used without prior written permission.

During week 12 (84-91 days after randomization). German sites only will have an X-ray completed instead of a CT or MRI for the week 12 assessment. If disease progression is suspected, a follow-up CT or MRI will then be completed

During week 16 (112-119 days after randomization)

Every 8 weeks thereafter until progression/ start of further treatment.

After approval of protocol version 3, tumour assessments to be performed every 18 weeks unless clinically indicated until progression or start of further treatment.

13. Confirm adherence to study medication and supportive care for adverse events noted in [Section 4.1.4](#)
14. Collection of information on progression, further anti-cancer treatment and death. Information should be collected from the patient notes or by telephone contact with the patient. In countries where regulations allow, public records may be utilized to assess the mortality status for patients lost to follow up or where mortality information is not readily available through 3 attempted contacts. A formal study visit is not required. Once Protocol Version 3.0 is final (and where required locally, approvals are obtained by the site as per Section 8.1), the collection of Observation Period data will no longer be required.

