### **3.3 SELECTION OF TRIAL POPULATION**

Approximately 800 patients will be randomized at approximately 200 study sites globally. The study will be conducted in approximately 24 countries. The rate of randomization will vary by study site, but is expected to be approximately 2-15 patients per site.

A log of all patients included into the study (i.e. having given informed consent) will be maintained in the ISF at the investigational site irrespective of whether they have been randomized into the trial or not.

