##### 3.3.4.1.1 Patient discontinuation of study participation

A patient who has discontinued study drug for any of the reasons listed above except reason 5 (i.e. study drug toxicity), will complete a FUP visit and then continue in the Observation Period of the study for vital status and anti-cancer treatment monitoring. Patients who discontinue study drug due to any reasons other than 2 or 3 above will continue to have tumour assessments until disease progression or start of new anti-cancer therapy, following the same schedule Observation Period assessments will be completed as indicated in the [Flow Chart](#). Once Protocol Version 3.0 is final (and where required locally, approvals are obtained by the site as per [Section 8.1](#)), the collection of vital status data will be ceased.

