##### 5.1.2.1.1 Central imaging

All image data will be sent to a central imaging unit to obtain an independent blinded confirmation of tumour response assessment based on a uniform interpretation of radiographic image data for all patients enrolled in the trial. Upon receipt, the central imaging unit will log all image data into a tracking system and perform quality control of digitised radiographic images. An independent review of radiographic images including (i) sequential lesion selection and measurement and (ii) incremental radiological response assessment followed by (iii) global review of tumour response or progression will be performed by two blinded (with regard to patient, treatment, and visit) radiologists. In the case of disagreement on the radiological assessment at any timepoint between the two primary reviewers, a third

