## 10. APPENDICES

### 10.1 RECIST 1.1 CRITERIA

The criteria below are based on RECIST 1.1 ([R09-0262](#)).

The preferred method of assessment is a spiral CT scan with IV and oral contrast, unless IV and/or oral contrast are medically contraindicated. CT scans of the chest, abdomen and other areas of known or newly suspected disease must be performed. Scans of the abdomen, pelvis and other areas of the body, but not chest, may be done with MRI instead of CT.

Skin lesions followed as target lesions must be documented by colour digital photography and must include in the image a ruler with millimetre subdivisions and a label that includes the patients ID and date.

Bone scans (using m-technetium polyphosphonate scintigraphy) are recommended at baseline if the patient has any signs and symptoms consistent with bone metastasis or a history of bone metastasis. Bone metastasis identified at baseline must be documented and assessed according to RECIST 1.1 at the times of the other tumour measurements indicated in the [flow chart](#). During the study bone scans should be repeated as clinically indicated in patients without bone metastasis at Baseline.

For the purposes of this study, patients should be re-evaluated for response at weeks 8, 12, 16, and every 8 weeks thereafter. In the event of a treatment delay, interruption or discontinuation of treatment, tumour assessment should continue to follow the original schedule.

After approval of protocol version 3, tumour assessment will be performed every 18 weeks unless clinically indicated until progression or start of further treatment.

Follow-up tumour assessments must utilize the same CT/MRI/photographic method and acquisition technique (including use or non-use of IV contrast) as were used for screening assessments to ensure comparability. A chest x-ray or skeletal x-ray which clearly demonstrates a new metastatic lesion may be used to document progression in lieu of CT/MRI/bone scan.

Only those patients who have measurable disease present at baseline, have received at least 3 weeks of therapy, and have had their disease re-evaluated will be considered evaluable for response. These patients will have their response classified according to the definitions stated below.

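### Does a German week-12 visit with X-ray only count as missed in the PFS censoring rules, and does it matter?

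*SAP*

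**What the plan says.** Flow chart footnote 12 of the protocol sets tumour assessments at weeks 8, 12 and 16 and then every 8 weeks, with one national exception: "German sites only will have an X-ray completed instead of a CT or MRI for the week 12 assessment". The next sentence adds: "If disease progression is suspected, a follow-up CT or MRI will then be completed". The SAP repeats both in Section 6.7 and closes with "In the case where a CT or MRI is not completed for the week 12 assessment, it will be handled as missing assessment". That paragraph opens with a limited scope: "For the presentation of tumour response data which will follow a calculated visit approach".

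Three other places bear on the point.

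- SAP 6.6 states that patients with missing tumour imaging are censored in time-to-event analyses and leaves the details to Section 7.
- Table 7.4: 1, the same in Protocol 7.4 and SAP 7.4, counts missed assessments. After a non-PD scan, one missed assessment still allows an event (rule 3b). More than one in a row leads to censoring at the last imaging before the gap (rule 3c). New anti-cancer therapy before progression also leads to censoring at the last imaging (rule 4). The table neither defines a missed assessment nor mentions X-rays.
- Protocol Appendix 10.1 says of a chest or skeletal X-ray that one "which clearly demonstrates a new metastatic lesion may be used to document progression in lieu of CT/MRI/bone scan". It makes no exception for Germany or for week 12.

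**The concern.** A visit carried out exactly as the protocol orders is labelled missing. If that label carries into Table 7.4: 1, a German patient has used up the one tolerated gap by week 12 without any departure from the schedule. If it does not carry over, the same patient still has it. The table does not say which, and it governs the primary endpoint in both the central and the investigator reading.

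There is also an apparent conflict. A German patient whose week-12 X-ray shows a clear new metastasis, with no CT or MRI afterwards, has documented progression under Appendix 10.1 but a missing visit under SAP 6.7. Protocol 3.3.4.1.1 does not require imaging to continue after radiologically documented progression: "Patients who discontinue study drug due to any reasons other than 2 or 3 above will continue to have tumour assessments until disease progression", where reason 2 is radiologically documented progression. If new therapy then starts, rule 4 could censor this patient at week 8 instead of counting an event at week 12.

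**Working it through.** **1. Where the reading changes a classification.** Take a German patient with a non-PD CT at week 8 and only an X-ray at week 12.

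| What happens next | X-ray visit counted as missed | Not counted as missed |
|---|---|---|
| PD on the week-16 CT | event | event |
| Death between weeks 12 and 16 | event (3b) | event (3a) |
| Week-16 scan missed, death in week 21 | censored at week 8 (3c) | event (3b) |
| Clear new lesion on the X-ray, no CT/MRI, new therapy started | censored at week 8 (rule 4) | event at week 12, if read as PD |

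The ordinary courses agree. A difference needs a second missed scan, or an X-ray with clear PD that no CT or MRI follows.

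**2. Which reading the text favours.** SAP 6.6 says missing tumour imaging is censored in time-to-event analyses, and 6.7 then says which week-12 visit is missing. Both stand under general analysis definitions. Counting the visit as missed is the likelier reading, although it is inferred. For the fourth row, footnote 12 already asks for CT or MRI once progression is suspected, and a clear new lesion is at least that. Central review also receives the films: "All image data will be sent to a central imaging unit".

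**3. The plan's own figure.** For HR = 10/14, two-sided alpha 0.05, 90% power and 1:1 allocation (Protocol 7.6), d = 4(1.960 + 1.282)² / (ln(10/14))² = 42.03 / 0.1132 = 371.2, so 372 as stated. Power at 372 is Φ(√372/2 × 0.3365 − 1.960) = Φ(1.285) = 90.1%.

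**4. Patients exposed at the PFS analysis.** The analysis takes place at 372 events, not after full follow-up of 800 patients. With accrual r per week and hazard λ = ln 2 / median in each arm, expected events by time T are the sum over arms of (r/2)[T − (1 − e^(−λT))/λ], assuming exponential PFS and no dropout.

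- r = 6 per week: T = 79.1 weeks, 474 randomised, 6 × (79.1 − 12) ≈ 402 past week 12 and 6 × (79.1 − 24) ≈ 330 past week 24.
- 36 per month (8.28 per week): T = 61.7 weeks, 511 randomised, about 411 past week 12 and 312 past week 24.

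**5. German share.** It is not stated. Protocol 3.3 says: "The study will be conducted in approximately 24 countries". An equal share is 1/24 = 4.2%; I assume 4–10%.

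**6. Size of the two routes.** Time to PD is exponential with median 10 or 14 weeks. Survival after PD is exponential with an assumed median of 6, 12 or 18 weeks.

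- Clear PD on X-ray without CT/MRI: P(PD in weeks 8–12, alive at 12) = 0.096–0.128. Assume 5–20% of these are X-ray only. Low: 0.096 × 402 × 0.04 × 0.05 = 0.08. High: 0.128 × 411 × 0.10 × 0.20 = 1.05. This is generous: a patient who starts no new therapy and dies before week 16 is an event either way.
- Week-16 scan also missed (assumed 5–20%), then death: P(PD after week 12, death in weeks 20–24) = 0.027–0.056. This gives 0.027 × 312 × 0.04 × 0.05 = 0.02 to 0.056 × 330 × 0.10 × 0.20 = 0.37. Counting deaths from week 17 (0.042–0.093) gives 0.03–0.61.

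Together: 0.1 to 1.4 events, or up to 1.05 + 0.61 ≈ 1.7 on the wider window, which is 1.7/372 = 0.5%.

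**7. A cruder bound for any route.** One further route, a missed week-8 scan, an X-ray at week 12 and PD at week 16, is outside that sum. If 2–10% of events are German and 5–15% of those are reclassified by any route, 372 × 0.02 × 0.05 = 0.4 to 372 × 0.10 × 0.15 = 5.6 events are lost. At 366.4 events power is 89.6%.

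**The case for a change.** The best argument for acting is one of principle. The trial is open-label, and Protocol 3.2 says each patient's treatment is known in the eCRF. A rule that decides events for the primary endpoint should not rest on inference. The lead-in to SAP 6.7 does confine the paragraph to the presentation of response data, and an X-ray that was taken is not a missed radiologic assessment in ordinary language. One footnote would settle it.

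What stands is that the wording is open and a cross-reference from the table to SAP 6.7 would have been tidier. The technical TSAP that SAP 7.8.1 mentions is not available here and may already contain it.

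The case for a substantive change does not stand. Either reading is defensible. Counting the visit as missed fits a centrally read endpoint: the patient who dies in week 21 was last seen on CT 13 weeks before, and rule 3c exists for such gaps. Taking week 12 out of the German schedule would let a death count up to 16 weeks after the last CT (week 8 to week 24), against 8 weeks elsewhere after a week-8 scan. It would also shift the second scheduled assessment in rules 1, 6a and 6b from week 12 to week 16 for one country. With P(death in weeks 12–16) = 0.058–0.125 and an assumed 5–10% never imaged, that reclassifies about 0.058 × 402 × 0.04 × 0.05 = 0.05 to 0.125 × 411 × 0.10 × 0.10 = 0.5 deaths, which is comparable with the problem itself.

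**Conclusion.** This is a gap in wording that analysts can fill sensibly from SAP 6.6 and 6.7, and it calls for no change to the plan. The two main routes touch roughly 0.1 to 1.7 of 372 PFS events. Even 5.6 lost events leave power at 89.6%, and because the analysis is triggered by events, later ones would normally make up the number. The same rule applies to both randomised arms, and nothing in the documents suggests that it favours either.

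The figures rest on assumptions that the documents do not supply: German enrolment of 4–10%, 5–20% for missed scans and for clear X-rays without CT or MRI, and survival after progression with a median of 6–18 weeks. None of these would need to be exact for the conclusion to hold. The second amendment's rationale in Protocol Section 11 also records that PFS has been assessed and reported, so a new rule now would gain nothing.

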7. PLANNED ANALYSIS

For End-Of-Text (EoT) tables, the set of summary statistics is: N / Mean / SD / Min / Median / Max. For appendix tables, the set of summary statistics is: N / Mean / s.d. / Min / Q1 (lower quartile) / Median / Q3 (upper quartile) / Max.

Tabulations of frequencies for categorical data will include all possible categories and will display the number of observations in a category as well as the percentage (%) relative to the respective treatment group (unless otherwise specified, all patients in the respective patient set whether they have non-missing values or not). Percentages will be rounded to one decimal place. The category missing will be displayed only if there are actually missing values.

7.1 DEMOGRAPHIC AND OTHER BASELINE CHARACTERISTICS

Only descriptive statistics are planned for this section of the report.

7.2 CONCOMITANT DISEASES AND MEDICATION

Descriptive statistics using standard summary tables for the randomised set of patients are planned for this section of the report.

7.3 TREATMENT COMPLIANCE

Descriptive statistics using standard summary tables for the treated set of patients are planned for this section of the report. A summary of whether patients took their treatment according to the protocol and whether they missed any doses will be produced for each planned visit. In addition a summary of overall percentage compliance will be produced using visit dates and the total number of doses missed during the study.

